eligible will be invited to an informed consent meeting. Post-consent a baseline survey will be sent electronically and once completed, a pain assessment will be conducted by a registered nurse (the PI, a certified pain management RN) via telehealth. Each participant will be asked to choose two treatment modalities for a consultation and brief trial and schedule a weekly 45-minute appointment for six weeks; individuals will receive three rounds of the two different modalities they choose using a shared-decision making process that allows guidance by research staff who are knowledgeable about the therapy selection. Data will be collected in multiple ways including via healthcare practitioners (e.g. McCaffery Initial Pain Assessment Tool, Functional Rating Index, etc.), participants (e.g. surveys for demographic information, health history, pain level, satisfaction, and medication usage), study staff (e.g. attendance records) and from clinical records (medication dose prescribed) using IRB-approved protocols. An exit interview will be audio-taped to capture more specific information about patient experiences. See Data Collection Plan table below. Data will be analyzed using descriptive summary statistics, paired t tests for pre and post-test effect size calculations, and content analysis for qualitative data. Sample size of 30 was chosen based on the number needed to generate sufficient pilot data to calculate effect sizes for future trials (Jacobsen & Melnyk, 2012).

All study activities including the informed consent meeting will be completed using telehealth principles using Zoom technology and/or telephone. Participant will review consent document and be informed that consent is implied by completion of the initial baseline survey. No signatures will be collected but the participant will receive a mailed or emailed copy of the consent. We will use WSU-licensed Zoom accounts.

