### **Data collection plan**

Measure	T1	T2	T3
	Week 0	Week 3	Week 6
Baseline Measures			
Demographics & Medical History	✓		
Modality Selection Questionnaire	✓		
McCaffery Pain Assessment (by RN)	✓		✓
Functional Index (by RN)	✓		
Medication goal	✓	✓	✓
Primary Self-reported Outcomes			
Pain Intensity and Pain Interference (PROMIS)	✓	✓	✓
Self-efficacy of Symptoms/Emotions (PROMIS)	✓	✓	✓
Current Opioid Misuse Measure (COMM)	✓	✓	✓
Depressive Symptoms (PHQ-8)	✓	✓	✓
Anxiety (GAD)	✓	✓	✓
Spiritual Well-being Scale	✓		✓
Interpersonal Needs Questionnaire	✓	✓	✓
Additional Data			
Program Satisfaction Questionnaire		✓	✓
Post Program Interview			✓
Program Engagement (program attendance records)	✓	✓	✓
Medication Dose (clinical record)	✓		✓

Data collection will be taken at baseline, Week 3 and Week 6.

**Cultural Competency: (For projects involving select populations, provide the researchers' qualifications for working with the subjects.)**

The PI has conducted 10 studies on chronic pain populations and has received specialized training and certification in pain management nursing.

2. What will each participant be asked to do in their role as a participant?

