Interested participants will agree to be screened for project eligibility via telephone after receiving study information; if deemed eligible, participants will be asked to attend an informed consent meeting with study staff held over phone or Zoom videoconferencing that will last about 1 hour. After consent a registered nurse will conduct a thorough pain assessment on each participant guided by the McCaffery Initial Pain Assessment Tool and the Functional Rating Index (20 min). The participants will be asked to choose one non-opioid treatment modality (selecting from yoga, physical therapy, massage or chiropractic therapy). After selection of the treatments, participants will be asked to schedule and attend six treatment appointments (three sessions of 2 different modalities) over the course of six weeks. Prior to the first assessment by the nurse, participants will be asked to complete a baseline survey via Qualtrics electronic survey that includes baseline demographic and health history information as well as create one goal related to their prescribed opioid use (e.g. reduce their dose or avoid a dose increase). Participants must be willing to attend treatment sessions that last for 45 minutes weekly and take place primarily using Zoom videoconferencing and phone back-up. Attendance at each scheduled appointment will be logged and participants will be asked to complete surveys after

each modality trial focused on satisfaction, pain level, symptoms, and medication usage (see Appendix for survey items). At the end of the six week study period an exit interview via phone of 60 minutes or less will be conducted with each participant which will include questions related to identifying their preferences and the challenges they experienced with each treatment modality, goal setting/achievement, and the COMFORT process as well as their desire and likelihood of continuing each treatment option they trialed during the project. Because we are using telehealth, all “treatments” will be guided by the practitioner, representing a consultation and educational experience versus a “hands-on” treatment approach that would normally be used in person. Eg. Chiropractor may assist in teaching posture awareness by watching the person walk and giving advice, and massage therapist may have participants use tennis balls to roll on painful areas to simulate massage – these are activities within the practitioners’ usual scope and range of patient educational activities.

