**Check all that apply. Submit a copy of all the materials that will be used.**

Person to person solicitation

Snowball sampling

Phone

Postal mail

E-mail

Poster

Media (TV, newspaper, radio, web site, social media) Specify:

IRB Approved Listserv:

Subject Pool or Recruitment Pool:

Other:

None (e.g., for studies using existing specimens or secondary data)

2. How will potential subjects be identified? How will potential subjects be approached? Answer for each subject group.

Explain in detail: We will recruit up to 30 participants from the CHAS clinics in the Spokane region who are prescribed any opioid for any chronic, non-cancer-based painful medical condition (greater than 3 months) and report at least moderate (5) pain symptoms on the Numeric 0-10 Pain Scale.

Clinic staff will provide potential participants a study flyer either in person if they are in clinic or electronically if seen in telehealth visit and ask if they would like to be contacted with further information (Appendix 1). Potential participants will have the option of contacting research team members directly using a private voice mail. A standardized script will be used to guide the invitation and limit coercion that states: (Appendix 1). If potential participants agree, they will receive a copy of the informed consent and will be asked if they wish to be screened for eligibility. Research assistants who have received training in screening will proceed with the screening process. If determined to be eligible and they agree, participants will be contacted by a member of the research team for the informed consent process. Their preferred contact information will be collected on a HIPAA-compliant form that will remain secure at their facility's office until the information is relayed to the researchers by phone or in person. Potential participants may choose to contact researchers on their own using the contact information on the informed consent.

Flyers will be made available for distribution to the clinic staff for internal communications or to be posted in public view at the discretion of each facility's administration team (Appendix).

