Psychological/ emotional discomfort/distress:

Participants will be told on informed consent about potential psychological risk with these statements: "It is possible you will feel stress or psychological discomfort when you are answering personal questions or engaging in any of the non-drug treatment options. You are encouraged to contact any member of the study team if you feel you need additional counseling or other support, and we will refer you to the appropriate services."

Physical harm/discomfort/:

Occasionally, participants may have adverse effects from any one of the chosen non-drug treatment options such as pain, muscle strain, or increased fatigue. These risks will be reduced through the screening histories, physical exam by each treatment provider, and your own communications with providers about your body and preferences. You will not be forced to do anything you are not comfortable doing or believe may cause you harm.

We have chosen experienced providers to provide treatments who have many years of evaluating patients and who will take every precaution to preserve your safety and well-being.

Significant time: Recognizing that this study entails significant time, we will provide each participant with a written schedule and be sure they understand the time commitment prior to consenting. We will allow flexibility in certain aspects of the study when feasible, such as the appointment days and times and provide reminder calls..

5. In the event that any of these potential risks occur, how will it be handled (e.g. compensation, counseling, etc.)? Include supporting materials.

Explain in detail:

Privacy/confidentiality: Known breaches of confidentiality will be reported to participants and researchers will make every attempt to assure future data protections. Conversations will occur in private areas as much as possible. Medical and eligibility screenings will take place in private.

Psychological/ emotional discomfort/distress: As informed in the consent process, if the study staff learns that depression screening or other study data suggests the possibility of severe or

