higher depressive symptoms (as defined by the PHQ-9 guidelines) or participants indicate any suicidal, homicidal, or self-harm plan, that information will be reported to the study medical director and primary provider of record. Participants will be encouraged to seek a professional evaluation and be given a number for the suicide hotline. Research personnel and treatment providers will be trained to notify the PI or study physician if any psychological or emotional distress is noted. The primary investigator or licensed co-investigator will be available at all times to provide advice and intervene as necessary. The participating treatment providers will be given directions on how to handle unexpected medical or mental health events.

**Physical harm/discomfort:** Participant comfort will be assessed after each study treatment session and opportunity will be available to minimize any immediate adverse events. All treatment sessions will be delivered by trained and experienced licensed providers and any problems dealt with using usual procedures that are standard for their professions (see letters of commitment in Appendix), such as stopping treatment when necessary and initiating emergent care (calling 911). Providers will be trained to alert PI for adverse events such as physical symptoms of agitation, increased pain, nausea, tremors, etc. A physician and/or licensed healthcare provider with relevant experience with pain populations (RN, MD) will be available at all times via phone during the treatment sessions to trouble-shoot any adverse events or unexpected responses. If deemed necessary, participants will be seen by a licensed healthcare provider for evaluation. Participants are informed during consent process that they or their health insurance will be responsible for costs if any additional medical or psychological services are needed. The study team will assist in connecting them with resources if needed using state sponsored services.

**Significant time:** If unexpected time delays occur due to scheduling conflicts or other unanticipated delays, the PI will express appreciation and offer apologies with an additional \$10 gift card as a thank you for additional time spent.

6. Is it possible that you will discover a subject's previously unknown physical or psychological condition (e.g. disease, depression, suicidal ideation, genetic predisposition, etc.) as a result of your procedures?

YES

NO

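### Comfort is assessed only after each session, with no value before it and no question about the days between, so worsening linked to a session cannot be separated from existing pain

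*Combined protocol and SAP*

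**What the plan says.** Section 8, item 5 (physical harm/discomfort) sets out the session-level check: "Participant comfort will be assessed after each study treatment session and opportunity will be available to minimize any immediate adverse events". It goes on: "Providers will be trained to alert PI for adverse events such as physical symptoms of agitation, increased pain, nausea, tremors, etc". It names no scale, reference value or time window for increased pain. Clinical backup by phone is described for the time the sessions are running.

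Section 8, item 4 lists the expected physical harms: "Occasionally, participants may have adverse effects from any one of the chosen non-drug treatment options such as pain, muscle strain, or increased fatigue".

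Section 6, item 2 describes recruits as people who "report at least moderate (5) pain symptoms on the Numeric 0-10 Pain Scale". The numbered eligibility criteria in the same item do not repeat this.

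Section 2, item 2 has participants "schedule and attend six treatment appointments (three sessions of 2 different modalities) over the course of six weeks". Attendance at each appointment is logged, and surveys covering pain and symptoms follow each modality trial. Under the data collection table, the plan states: "Data collection will be taken at baseline, Week 3 and Week 6".

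**The concern.** Increased pain and increased fatigue describe a change, and recognising a change takes two observations or a direct question about change. The plan describes one observation, made afterwards, in people recruited because they already have substantial pain. The check is also directed at immediate events, whereas nothing in Section 8 confines pain, strain or fatigue to the session itself.

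The study pilots remotely guided versions of therapies that are normally hands-on. Whether a session leaves people worse, at once or over the following days, is basic information for planning a later trial. If it is not recorded session by session, it cannot be reconstructed afterwards.

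**Working it through.** The plan states no figure on this point, so there is none to reproduce. The check is a count of measurement occasions and a reading of the relevant sections side by side.

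**Inputs**
- Participants: 30 (Section 5, item 1).
- Sessions per participant: 6, three of each of two modalities (Section 2, item 2).
- Interval: one week (Section 2, item 1, Procedures: "schedule a weekly 45-minute appointment for six weeks").
- Scheduled pain measurement points: 3 (Weeks 0, 3 and 6; Data collection plan).

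**Coverage**
- Sessions: 30 × 6 = 180.
- Scheduled participant pain measurements: 30 × 3 = 90.
- Measurements specified as taken just before a session on the same day: 0.

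**What the post-session check can show.** Write post-session pain as starting pain plus change during the session. Only the left side is observed. Section 8, item 5 names no scale, so this is only an illustration: a participant at 6 afterwards has worsened by 1 if the start was 5, is unchanged if it was 6, and has improved by 1 if it was 7. All three starting values satisfy the recruitment description. The Week 0 and Week 3 values do not settle which applies, because they are not taken at the session.

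**What happens to later symptoms.** Four routes are described:

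| Route | Where | Asks about symptoms? | Tied to a session? |
|---|---|---|---|
| Post-session comfort check | Section 8, item 5 | Yes, aimed at immediate events | Yes |
| Next weekly contact with a provider | Section 2; Section 8, item 4 | Only informally | Not recorded as such |
| Survey after each modality trial | Section 2, item 2 | Yes | No, covers three sessions |
| Exit interview | Section 2, item 2 | Preferences and challenges by modality | No |

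Assume that each modality's three sessions run consecutively, which fits the Week 3 and Week 6 surveys. A symptom that starts after the first session of a block then waits 2 × 7 = 14 days until the third session. If the survey comes up to a week later, the wait for a structured question is about two to three weeks. By then, three sessions are candidate sources.

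**The case against.** The strongest reply is that the plan describes clinical observation and sets no scoring rule. Comfort is to be assessed, with no number named. Increased pain is one example in a list with agitation, nausea and tremors. A licensed practitioner is live with the participant for 45 minutes and can simply be told that pain has risen, so an alert is possible without a starting score. That is right, and it rules out the reading that the alert cannot work.

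A reader might also infer that later-onset harm goes undetected. The documents do not support this. Providers see participants weekly, the surveys after each modality trial ask about pain and symptoms, and Section 8, item 6 has the principal investigator review survey health information and follow up concerns. Such symptoms are captured late and unsystematically.

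A reader might further want a false-alert rate. None can be derived: the plan gives no standard deviation, no threshold for a rise and no comparison with the previous week's value.

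Three other points limit the claim. The survey items and the providers' letters of commitment are in appendices that were not available, so a pre-session item there cannot be excluded. The pain level of 5 is in the recruitment text but not in the numbered criteria. A per-session rate of worsening is not a declared aim of the pilot.

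What remains is that nothing in the supplied text obtains a starting value or asks about the interval between sessions. The informal routes leave no described record from which session-related worsening could be summarised.

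**Conclusion.** The point holds as a measurement gap. Followed as written, post-session-only assessment cannot separate session-related worsening from pain already present, in any of up to 180 sessions. Strain or fatigue that begins later is not linked to a session and may wait about two to three weeks for a structured question.

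This rests on three assumptions: the appendices contain no pre-session or since-last-session item, each modality's sessions run as a block, and some of the named harms can begin after a session ends. The conclusion does not extend to how often harm occurs or how often an alert would be wrong. It is a modest point, but worth acting on before the first session because the information cannot be recovered later.

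**What to change.** Add three fields to the session log:
1. A 0-10 pain rating at the start of the session.
2. The same rating at the end.
3. From the second session on, one start-of-session question on new pain, strain or fatigue since the last session.

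Repeat the third item at the Week 6 contact to cover the final session, and record the date so that the elapsed time is known. If an appendix already holds such items, cite it in Section 8 and in the data collection table.

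Report within-session change and between-session symptoms descriptively, by participant and modality. With one group and no control, neither should be presented as a treatment effect.

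With full attendance this gives 180 start-end pairs. It also gives 30 × 5 = 150 between-session answers plus 30 at Week 6, so every session is followed by one question. The cost is about one minute per session from the provider already present: 180 minutes (3 hours) over the study, or 6 of each participant's 6 × 45 = 270 session minutes (about 2%).

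This concerns recording only. What counts as an alert, and whether treatment changes as a result, are for the investigators to decide.

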## SECTION 9. Research Involving Potential Reportable Activity

1. Will the project involve the potential discovery of child abuse?

Yes  No

If yes, there are legal obligations to disclose to the proper authorities certain information about reportable activities obtained during research. This obligation and intended course of action must be communicated to the participants in the consent form.

## SECTION 10. Research Involving Deception

1.  Yes  No Will any information be purposely withheld from the participants or will they be given any misinformation?

If yes, this will require alteration of informed consent process. Complete Addendum 4 and submit along with the application.

2. Why is the deception necessary?

Explain in detail:

3. How and when will the subjects be debriefed after the project? Attach debriefing script.

Explain in detail:

## SECTION 11. Research Involving Health Insurance Portability and Accountability Act (HIPAA)

Address the following questions regarding the use of protected health information:

1.  Yes  No Will health information be obtained from a covered entity (a health care provider who bills health insurers e.g., WSU Cougar Health Services)?
2.  Yes  No Does the research involve the provision of healthcare in a covered entity, such as WSU Cougar Health Services?
3.  Yes  No If the study involves the provision of healthcare, will a health insurer or billing agency be contacted for billing or eligibility?
4.  Yes  No Does the research involve use or creation of protected health information?

If no, to all the questions above you are not subject to HIPAA.

If yes, to any of the questions above complete **Addendum 7** and submit with the application. Please be advised that HIPAA protected data cannot be stored in the cloud per WSU policy.  
<https://security.wsu.edu/policies-and-guidelines/>.

## SECTION 12. Research Involving Investigational Drugs, Devices, Alcohol, Blood, Tissue, Bodily Fluids or other Biological Specimens

1.  Yes  No Will any investigational new drug (IND) be used?  
If yes, complete **Addendum 8** and attach it to the application.
2.  Yes  No Will any other drugs be used?  
If yes, complete **Addendum 8** and attach it to the application.
3.  Yes  No Will any investigational device (IDE) be used?  
If yes, complete **Addendum 8** and attach it to the application.
4.  Yes  No Will alcohol be ingested by the subjects?  
If yes, describe what type and how it will be administered:

 The Administrative Simplification standards adopted by Health and Human Services (HHS) under the Health Insurance Portability and Accountability Act of 1996 (HIPAA) apply to any entity that is

- a health care provider that conducts certain transactions in electronic form (called here a "covered health care provider").
- a health care clearinghouse.
- a health plan.

An entity that is one or more of these types of entities is referred to as a "covered entity" in the Administrative Simplification regulations.

 Protected health information is individually identifiable health information used by HIPAA-covered entities and their business associates in the relation to the provision of healthcare.

 "Drug" definition: <https://www.fda.gov/drugs/informationondrugs/ucm079436.htm>, WSU Cannabis Research Policy: <https://orso.wsu.edu/documents/2018/02/guideline-15.pdf/>

 Refer to the guidelines for administration of ethyl alcohol in human experimentation (OGRD Memo No. 18 <http://www.orso.wsu.edu/documents/2018/02/guideline-18.pdf>) and NIAAA.

